9.1.4 Censoring rules for time to radiological progression

Note: ‘radiological’ in the tables refer to either ‘radiological soft tissue’ or ‘radiological bone’ as applicable to the endpoint.

Refer to Section 4.5.2 for pooling cut-off date.

Table 9–5 applies to:

- **Time to radiological progression following randomization**
- **Time to radiological bone progression following randomization and**
- **Time to radiological soft tissue progression following randomization.**

The following censoring rules will be used for both Comparison 1 and Comparison 2. Randomization baseline is used for all comparisons.

Table 9–5 Censoring for Time to Radiological Bone/Soft Tissue Progression following randomization

Situation	End Date	Censored	Reason for Censoring
No randomization baseline or post-randomization baseline radiological assessment	Date of randomization	Yes	No baseline or post-baseline assessment.
Subject died without prior radiological progression	Date of last radiological assessment before death	Yes	No progression before death or database cutoff
Subject survived without radiological progression as of database cutoff date	Date of last radiological assessment before data cutoff	Yes	Alive and no progression before database cutoff
Subject had a radiological assessment of PD (no two consecutive missed radiological assessments*)	Date of first PD	No	N/A
PD immediately after two or more consecutive missed radiological assessments*	Date of last radiological assessment before missed assessments	Yes	Missed two or more consecutive tumor assessments
Subject discontinuation from study for reasons other than PD	Last radiological assessment date	Yes	Subject discontinued from study due to a reason other than PD
Subjects discontinued from study due to PD, but no documented date of PD	Date of last radiological assessment	Yes	Subjects discontinued from study due to PD, but no documented date of PD
New non-protocol permitted systemic anti-cancer treatment started	Date of last radiological assessment before starting new systemic anti-cancer treatment	Yes	New anti-cancer treatment started

*Two consecutive missing radiological assessments are defined as the time interval between two consecutive radiological assessments is more than 28 weeks = $2 \times (12+2)$ week, where 12-week is scheduled frequency for tumor assessment and 2-week is protocol-allowed window.

Duration = End date – randomization date +1

There will be no Week 24 baseline censoring for Comparison 2.

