In addition to the rules in [Table 9–5](#) the following rule will be applied to Comparison 1:

Situation	End Date	Censored	Reason for Censoring
Arm C subject with no radiological progression event on or after pooling cutoff date	Last radiological progression assessment on or before pooling cutoff date	Yes	Post Week 24 Arm C events censored at pooling cutoff date

When determining time to radiographic progression, the following rules will be applied by taking into consideration of both bone and non-bone disease status:

Table 9–6 Censoring for Time to Radiological Progression Following Randomization

Situation		Event/Censor	Event/censor date	Combined Non-bone and Bone outcome
1	Bone	Event (PD)	Bone scan date	Event at min(Bone scan date, Non-Bone assessment date)Event at min(Bone scan date, Non-Bone assessment)
	Non-Bone	Event (PD)	Non-Bone assessment date	
2	Bone	Censor	Bone scan date	Censor at min(Non-Bone assessment date, Bone scan date)
	Non-Bone	Censor	Non-Bone assessment date	
3	Bone	Censor	Bone scan date	Event at Non-Bone assessment date: if Non-Bone assessment date \leq Bone scan date ; Else if Non-Bone assessment date $>$ Bone scan date AND Difference $<$ 28weeks; Else censor at bone scan Date; Event at Non-Bone assessment Date: if Non-Bone assessment Date \leq Bone scan date Else if Non-Bone assessment Date $>$ Bone scan date AND Difference $<$ 28weeks Else censor at bscan Date
	Non-Bone	Event(PD)	Non-Bone assessment date	
4	Bone	Event(PD)	Bone scan date	Event at bone scan date: if Bone scan date \leq Non-Bone assessment date Else if Bone scan date $>$ Non-Bone assessment date AND Difference $<$ 28weeks; Else censor at Non-Bone assessment date
	Non-Bone	Censor	Non-Bone assessment date	

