9.1.5 Censoring rules for radiological progression-free survival (rPFS)

The following censoring rules will be used for both Comparison 1 and Comparison 2.

Table 9–7 Censoring for radiological progression-free survival following randomization

Situation	End Date	Censored	Reason for Censoring
No randomization baseline or post-randomization baseline radiological progression assessments	Date of Randomization	Yes	No baseline or post-baseline assessment.
Subject had a radiological assessment of PD following randomization (no 2 consecutive missing radiological assessments*)	Date of first radiological event	No	N/A
Death or PD immediately after two or more consecutive missed radiological assessments*	Date of last radiological assessment before missed assessments	Yes	Missed two or more consecutive tumor assessments
Subject discontinued from study for other than PD or death	Last radiological assessment date	Yes	Subject discontinued from study due to a reason other than PD or death
Death during the study (no 2 consecutive missing radiological assessments*) or before first radiological PD assessment	Date of Death	No	N/A
Subjects discontinued from study due to PD, but no documented date of PD	Date of last radiological assessment	Yes	Subjects discontinued from study due to PD, but no documented date of PD
Subject still on study at the time of data cutoff without PD	Last radiological assessment before data cutoff	Yes	Subject is still alive without PD
New non-protocol permitted systemic anti-cancer treatment started	Date of last radiological assessment before starting new systemic anti-cancer treatment	Yes	New systemic anti-cancer treatment started

*Two consecutive missing radiological assessments are defined as the time interval between two consecutive radiological assessments is more than 28 weeks = $2 \times (12+2)$ week, where 12-week is scheduled frequency for tumor assessment and 2-week is protocol-allowed window

Radiological progression date and status mentioned in above table will be obtained following the rules specified in [Table 9–6](#).

rPFS following randomization = End date – randomization date +1.

There will be no Week 24 baseline censoring for Comparison 2. Randomization baseline will be used for Comparison 2.

In addition to the rules in [Table 9–7](#), the following rule will be applied to Comparison 1:

Situation	End Date	Censored	Reason for Censoring

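### Table 9-6 removes event-free time after the earlier imaging date but keeps progressions found in that time, which pulls the per-arm progression curve down

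*SAP*

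**What the plan says.** Section 9.1.4 introduces Table 9-6 for time to radiological progression, where "the following rules will be applied by taking into consideration of both bone and non-bone disease status". Its four situations combine one bone result and one non-bone result:

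- Situation 1, both progressed: event at the earlier date.
- Situation 2, neither progressed: "Censor at min(Non-Bone assessment date, Bone scan date".
- Situations 3 and 4, one progressed: event at that progression's date if it is on or before the other modality's censor date, or less than 28 weeks after it. Otherwise the subject is censored at the other modality's date (situation 4: "Else censor at Non-Bone assessment date").

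Table 9-5 also lists the combined endpoint, "Time to radiological progression following randomization", and censors event-free subjects at the "Date of last radiological assessment before data cutoff" or, if they died, at the "Date of last radiological assessment before death". A note above it says that the word radiological in the tables may "refer to either ‘radiological soft tissue’ or ‘radiological bone’ as applicable to the endpoint".

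For rPFS, Section 9.1.5 states: "Radiological progression date and status mentioned in above table will be obtained following the rules specified in" Table 9-6. Table 9-7 nonetheless has its own row for subjects still on study without progression, which censors at the last radiological assessment before data cutoff.

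**The concern.** Situations 3 and 4 accept one modality alone as adequate follow-up for just under 28 weeks, provided that it shows progression. Situation 2 rejects the same single-modality follow-up when it shows none. Whether an interval counts as time at risk therefore depends on what was found in it. A censoring rule should not work that way: events stay in the numerator while the matching event-free time leaves the denominator, so the progression-free curve comes out too low.

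Section 6.2.2.2 tests time to radiological progression and rPFS in both comparisons and reports Kaplan-Meier medians and quartiles by group. Those per-arm summaries are what is mainly at stake.

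**Working it through.** **The window.** The footnote to Table 9-5 gives 2 × (12 + 2) = 28 weeks, which reproduces. Table 9-6 uses it as strictly less than 28 weeks.

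**Table 9-6 applied to one subject.** The last bone scan is at Week 24, without progression.

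| Later CT/MRI | Table 9-6 result |
|---|---|
| Progression at Week 36 | Event, Week 36 |
| Progression at Week 48 | Event, Week 48 |
| Clean at Week 48 | Censored, Week 24 |
| Progression at Week 52 (gap 28) | Censored, Week 24 |

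The second and third rows have identical imaging schedules and differ only in outcome, yet follow-up differs by 24 weeks.

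**Size.** The assumptions, none of which are in the SAP, are: exponential progression with median 40 weeks in bone and 80 weeks in soft tissue; bone scans at Weeks 8, 16, 24 and every 12 weeks after; a share f of 10% or 20% without soft-tissue reads, unrelated to prognosis. Loss is left out of the hand calculation.

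With complete reads the combined hazard is ln2/40 + ln2/80 = 3·ln2/80 per week, so:

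- S(24) = exp(−ln2 × 24 × 3/80) = 53.6%
- S(48) = exp(−ln2 × 48 × 3/80) = 28.7%
- Free of bone progression over 24 weeks: B = 2^(−24/40) = 66.0%, so 34.0% progress in bone

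*Soft tissue never read.* Take the soft-tissue date as randomization (Table 9-5, first row). Scans at Weeks 8, 16 and 24 all lie inside the window. Of the share f, only those with bone progression stay in the risk set, so the Week 24 estimate is (1−f)·S(24) / [(1−f) + f·(1−B)].

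- f = 10%: 0.4823 / 0.9340 = 51.6%, which is 2.0 points low
- f = 20%: 0.4287 / 0.8680 = 49.4%, which is 4.2 points low

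*Soft tissue stops after Week 24.* Bone scans at Weeks 36 and 48 are 12 and 24 weeks later, so the same ratio applies from Week 24 on.

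- f = 10%: 0.5359 × 0.5164 = 27.7%, which is 1.0 point low
- f = 20%: 0.5359 × 0.4939 = 26.5%, which is 2.2 points low

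Simulation with 3% monthly loss gave shortfalls of 1.9 and 4.4 points at Week 24, and 1.0 and 2.3 points at Week 48.

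**The same arithmetic with one window for events and non-events.** The share f is followed on bone alone for the window, so the estimate is (1−f)·S(24) + f·B, multiplied by S(24) for the Week 48 case.

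| Case | Complete reads | As written | One window |
|---|---|---|---|
| Never read, 10%, Week 24 | 53.6% | 51.6% | 54.8% |
| Never read, 20%, Week 24 | 53.6% | 49.4% | 56.1% |
| Stops after Week 24, 10%, Week 48 | 28.7% | 27.7% | 29.4% |
| Stops after Week 24, 20%, Week 48 | 28.7% | 26.5% | 30.0% |

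**Both events and censoring ended at the earlier date.** The share f then adds neither events nor time in the interval, and the estimate returns to S. The cost in the never-read case is f × 34.0%, that is 3.4 or 6.8 events per 100 subjects by Week 24.

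**The case against.** Four points have weight.

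*Censoring a composite at the last date on which both components were known is defensible.* It is, but only if events after that date are also left out. Table 9-6 does not do that.

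*Tables 9-5 and 9-6 need not conflict.* A reader might infer a flat contradiction. The title of Table 9-5 and the note on the word radiological suggest that it supplies component dates, which Table 9-6 then combines; Section 6.2.2.1 also sends the progression date to Table 9-6. Listing the combined endpoint under Table 9-5 is then largely a wording gap. The asymmetry inside Table 9-6 remains on either reading.

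*The size is easy to overstate.* Measured against following bone alone to the last scan, simulated Week 24 estimates with 20% never read were 49.5% and 56.2%, a gap of 6.7 points. That comparator treats unread soft tissue as progression-free, so it is itself too high; complete reads give 53.6%. With scattered single missed scans, late detection offsets the effect. In a separate illustrative run (combined median 8 months), the 48-week estimate as written was 0.381 with none missed and 0.387 with one modality missed at 40% of visits. A net downward bias is therefore shown for a modality that is absent or stops early, not for occasional misses.

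*The treatment comparison is nearly untouched.* With an assumed hazard ratio of 0.7 and equal discordance by arm, simulated values were 0.695 against 0.689 with complete data, and 0.720 against 0.708. A reader might infer a biased test; nothing in the SAP supports that unless discordance differs by arm.

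**Conclusion.** The rule is wrong as written for time to radiological progression: time at risk after the earlier modality date depends on outcome. Under the stated assumptions the per-arm curve falls short of complete reads by about 2-4 points at Week 24 (soft tissue never read in 10-20%) or about 1-2 points at Week 48 (reading stops after Week 24). The effect is zero when both modalities end on the same date. The true discordance rate is unknown, and the never-read case also assumes that a missing modality takes the randomization date, which Table 9-6 does not say.

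For rPFS the conclusion is conditional. A reader might infer the same bias there, but Section 9.1.5 imports progression date and status from Table 9-6 while Table 9-7 states its own event-free censor date. If Table 9-7 governs, situation 2 does not set that date. The two must be aligned. Little effect on hazard ratios is expected, and the co-primary SSE-FS is unaffected. The point should be corrected, but it does not threaten the main conclusions.

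**What to change.** Use one follow-up rule for events and non-events in Table 9-6:

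- Situation 2: censor at the last scan of either modality that is less than 28 weeks after the other modality's last date.
- Situations 3 and 4, progression at or beyond 28 weeks: censor at the last scan inside that window, not at the earlier modality's date.
- State that Table 9-5 gives component dates, that Table 9-6 governs the combined endpoint, and which table sets the event-free rPFS censor date.

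Censoring at the later date only when the gap is under 28 weeks, and otherwise at the earlier, is not enough: subjects with longer clean follow-up would still be cut back. In simulation with 20% stopping after Week 24, that version moved the Week 48 estimate only from 26.2% to 26.7%, against 28.5% with complete reads.

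The cost is SAP wording and one derivation. The drawback is single-modality follow-up for up to 28 weeks, which overstates progression-free time somewhat: by 0.7 to 1.3 points in three of the four cases tabulated and 2.5 points in the case of 20% never read. Each is smaller than the matching shortfall as written. Ending both events and censoring at the earlier date avoids the distortion in both directions if discordance is unrelated to prognosis. It loses observed events, so it suits a sensitivity analysis.

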9.1.5 Censoring rules for radiological progression-free survival (rPFS)

The following censoring rules will be used for both Comparison 1 and Comparison 2.

Table 9–7 Censoring for radiological progression-free survival following randomization

Situation	End Date	Censored	Reason for Censoring
No randomization baseline or post-randomization baseline radiological progression assessments	Date of Randomization	Yes	No baseline or post-baseline assessment.
Subject had a radiological assessment of PD following randomization (no 2 consecutive missing radiological assessments*)	Date of first radiological event	No	N/A
Death or PD immediately after two or more consecutive missed radiological assessments*	Date of last radiological assessment before missed assessments	Yes	Missed two or more consecutive tumor assessments
Subject discontinued from study for other than PD or death	Last radiological assessment date	Yes	Subject discontinued from study due to a reason other than PD or death
Death during the study (no 2 consecutive missing radiological assessments*) or before first radiological PD assessment	Date of Death	No	N/A
Subjects discontinued from study due to PD, but no documented date of PD	Date of last radiological assessment	Yes	Subjects discontinued from study due to PD, but no documented date of PD
Subject still on study at the time of data cutoff without PD	Last radiological assessment before data cutoff	Yes	Subject is still alive without PD
New non-protocol permitted systemic anti-cancer treatment started	Date of last radiological assessment before starting new systemic anti-cancer treatment	Yes	New systemic anti-cancer treatment started

*Two consecutive missing radiological assessments are defined as the time interval between two consecutive radiological assessments is more than 28 weeks = $2 \times (12+2)$ week, where 12-week is scheduled frequency for tumor assessment and 2-week is protocol-allowed window

Radiological progression date and status mentioned in above table will be obtained following the rules specified in [Table 9–6](#).

rPFS following randomization = End date – randomization date +1.

There will be no Week 24 baseline censoring for Comparison 2. Randomization baseline will be used for Comparison 2.

In addition to the rules in [Table 9–7](#), the following rule will be applied to Comparison 1:

Situation	End Date	Censored	Reason for Censoring
Arm C subject with no death or radiological progression event on or after pooling cutoff date	Last radiological progression assessment on or before pooling cutoff date	Yes	Post Week 24 Arm C events censored at pooling cutoff date

Title page

A three arm randomized, open-label Phase II study of radium-223 dichloride 50 kBq/kg (55 kBq/kg after implementation of NIST update) versus 80 kBq/kg (88 kBq/kg after implementation of NIST update) , and versus 50 kBq/kg (55 kBq/kg after implementation of NIST update) in an extended dosing schedule in subjects with castration-resistant prostate cancer metastatic to the bone

[Standard dose versus high dose and versus extended standard dose radium-223 dichloride in castration-resistant prostate cancer metastatic to the bone]

Bayer study drug BAY 88-8223 / Radium-223 dichloride / Xofigo

[Study purpose:] Efficacy, dose-finding

Clinical study phase: II **Date:** 02 July 2018

Study No.: BAY 88-8223 / 16507 **Version:** 1.0

Author: PPD

Confidential
The information provided in this document is strictly confidential and is intended solely for the guidance of the clinical investigation. Reproduction or disclosure of this document, whether in part or in full, to parties not associated with the clinical investigation or its use for any other purpose without the prior written consent of the sponsor is not permitted.

Throughout this document, symbols indicating proprietary names (®, TM) are not displayed. Hence, the appearance of product names without these symbols does not imply that these names are not protected.

This Statistical Analysis Plan is produced on a word-processing system and bears no signatures.
The approval of the Statistical Analysis Plan is documented in a separate Signature Document.

Table of Contents

Title page.....	1
Abbreviations.....	2
1. Introduction.....	2
2. Study Objectives.....	2
3. Study Design.....	4
4. General Statistical Considerations.....	4
5. Analysis Sets.....	4
6. Statistical Methodology.....	4
6.1 Population characteristics.....	4
6.1.1 Additional Summary of Baseline Characteristics.....	4
6.1.2 Additional Summary of Prior/Concomitant Bone Health Agent (BHA) use.....	4
6.2 Efficacy.....	4
6.3 Exploratory variables and analyses.....	5
6.4 Pharmacokinetics.....	5
6.5 Safety.....	5
6.5.1 Adverse Events.....	5
7. Document history and changes in the planned statistical analysis.....	5
8. References.....	5

Abbreviations

AE	Adverse event
BHA	Bone health agent
CI	Confidence interval
CSR	Clinical Study Report
SAP	Statistical Analysis Plan

1. Introduction

This Supplemental Statistical Analysis Plan (SAP) describes analyses that were not included in the main SAP but may be used for submission purposes or CSR.

This Supplemental SAP version 1.0 is a supplement of SAP version 2.0 dated 17 May 2017.

2. Study Objectives

Co-primary objectives:

Statistical Analysis Plan

Protocol No.: < BAY 88-8223/16507 >

Page: 3 of 5:

- To evaluate efficacy as measured by SSE-FS of radium-223 dichloride 50 kBq/kg (55 kBq/kg after implementation of NIST update) every 28 days for up to 6 doses compared to radium-223 dichloride 80 kBq/kg (88 kBq/kg after implementation of NIST update); and
- To evaluate efficacy as measured by SSE-FS of radium-223 dichloride 50 kBq/kg (55 kBq/kg after implementation of NIST update) every 28 days for up to 6 additional doses compared to no further radium-223 dichloride treatment in subjects with CRPC metastatic to the bone who previously received radium-223 dichloride 50 kBq/kg (55 kBq/kg after implementation of NIST update) every 28 days for up to 6 doses, and survived SSE free and are eligible for further radium-223 dichloride treatment.

Secondary objectives:

- To evaluate safety and tolerability
- To evaluate overall survival (OS)
- To evaluate pain improvement rate
- To evaluate time to pain progression
- To evaluate time to first SSE
- To evaluate time to radiological progression
- To evaluate radiological progression-free survival (rPFS)

Exploratory objectives:

- To evaluate quantitated whole body technetium-99 bone scan tumor burden area and index, and determine bone tumor response
- To explore the impact of patient body size on the efficacy and safety of radium-223 dichloride
- Time to increase in physical symptoms of disease based on the NCCN FACT-P Symptom Index-17 (NCCN-FACT FPSI-17) physical disease related symptoms (FPSI-DRS-P) subscale score measured up to Week 48 after the start of treatment
- To evaluate laboratory indicators of efficacy, including:
 - PSA response
 - Time to PSA progression
 - ALP response
 - Time to ALP progression
 - Percentage change in ALP from baseline
- To evaluate change in analgesic use.

3. Study Design

Refer to the main SAP v2.0 dated 17 MAY 2017.

4. General Statistical Considerations

Refer to the main SAP v2.0 dated 17 MAY 2017.

5. Analysis Sets

Refer to the main SAP v2.0 dated 17 MAY 2017.

6. Statistical Methodology

Refer to the main SAP v2.0 dated 17 MAY 2017.

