- The first bone scan with ≥ 2 new lesions compared to baseline is observed < 12 weeks from randomization and is confirmed by a second bone scan taken ≥ 6 weeks later showing ≥ 2 additional new lesions (a total of ≥ 4 new lesions compared to baseline); or
- The first bone scan with ≥ 2 new lesions compared to baseline is observed ≥ 12 weeks from randomization and the new lesions are verified on the next bone scan ≥ 6 weeks later (a total of ≥ 2 new lesions compared to baseline).

The date of progression of bone disease will be the date of the first observed bone progression, not the date that confirmed the bone progression.

The date of radiological progression will be determined following the rules in [Table 9–6](#).

Radiological progression-free survival is defined for each comparison as the time (days) from the randomization baseline to the date of radiological disease progression or death from any cause (if death occurs without prior progression). See [Table 9–7](#) in Appendix 9.1.5 for detailed censoring rules for both Comparison 1 and Comparison 2.

If data permits, unconfirmed radiological progression-free survival and time to unconfirmed radiological progression will be analyzed as sensitivity analyses based on central reviewer. Bone progression in this case does not require confirmation.

Pain endpoints

The pain data collected from ePRO will be used for these analyses.

Worst pain score (WPS) at a given visit is defined for each subject as the mean of the 7 day “worst pain score” assessments taken on or before each applicable visit. If less than 4 non-

missing WPS values are available for a given visit, then the weekly worst pain score will be left missing for that visit.

Timepoint pain improvement rate is defined with respect to each applicable baseline as the proportion of subjects with a 30% and 2-point decrease in WPS with respect to the applicable baseline assessment over 2 consecutive assessment periods conducted at least 3 weeks apart among subjects with a WPS score ≥ 4 at the applicable baseline. The first of the 2 consecutive periods is taken to be the date of improvement.

Time to pain progression is defined for each comparison in subjects with a WPS of ≤ 7 at the applicable baseline as the time from the applicable start date to an increase of 2 or more points in WPS (with respect to the applicable baseline). Refer to

Table 9–4 in Appendix 9.1.3 for detailed censoring rules.

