9.1 Censoring Rules

9.1.1 Censoring rules for Symptomatic Skeletal Event-Free Survival (SSE-FS)

Comparison 1:

- Arm C subjects who had SSE assessments or SSE event or death (in the absence of an SSE event) after ‘pooling cut-off date’ will be censored on last SSE assessment date prior to ‘pooling cut-off date’. Refer to Section 4.5 for pooling cut-off date.
- All other subjects in arms A, B and C, refer to [Table 9–1](#) for censoring rules.
- Symptomatic Skeletal Event Free Survival (SSE-FS) following randomization = End Date – Date of Randomization +1

Table 9–1 Comparison 1: Censoring for Symptomatic Skeletal Event Free Survival (SSE-FS)

Situation	End Date	Censored	Reason for Censoring
No post-randomization SSE assessment and no death	Date of Randomization	Yes	No post-baseline SSE assessments and no death
Subject had a SSE event	Date of first SSE	No*	N/A
Death without prior SSE (<13 weeks between last SSE assessment and death) #	Date of Death	No*	N/A
Death without prior SSE (≥ 13 weeks between last SSE assessment and death) #	Last SSE assessment before the missing SSE assessments#	Yes	≥ 13 weeks between last SSE assessment and death
Neither SSE nor Death by database cutoff date	Last SSE assessment prior to database cutoff	Yes	Neither SSE nor death

*The earliest end date in the table is used in calculating the SSE-FS.

#: use randomization date instead of last SSE assessment date if no post-randomization SSE assessment.

Note: symptomatic skeletal events immediately after missing SSE assessments are still counted as events in the analysis of SSE-FS.

Comparison 2:

- All subjects eligible for Comparison 2, refer to [Table 9–2](#) for censoring rules.
- Symptomatic Skeletal Event Free Survival (SSE-FS) following Week 24 baseline= End Date – Date of Week 24 baseline(the 6th dose date) +1

Table 9–2 Comparison 2: Censoring for Symptomatic Skeletal Event Free Survival (SSE-FS)

Situation	End Date	Censored	Reason for Censoring
No SSE assessment or death following Week 24 baseline	Date of Week 24 baseline	Yes	No post-Week 24 baseline SSE assessments and no

			death.
Had an SSE event between date of randomization and Week 24 baseline	Date of Week 24 baseline	Yes	First event occurred between date of randomization and Week 24 baseline
Subject had a SSE event after Week 24 baseline	Date of first SSE	No*	N/A
Death without prior SSE (<13 weeks between last SSE assessment and death) #	Date of Death	No*	N/A

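### Table 9-7 both censors at randomization and counts as an rPFS event a subject who dies without a post-baseline scan, and states no order of precedence

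*SAP*

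**What the plan says.** Section 6.2.2.1 of the SAP defines rPFS as the time from the randomization baseline to "radiological disease progression or death from any cause (if death occurs without prior progression"). Section 6.2.2.2 lists rPFS among the secondary endpoints tested in both comparisons, at a one-sided level of 0.10.

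Table 9-7 in Section 9.1.5 turns this definition into rules. Two rows matter here:

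- **Row 1**, "No randomization baseline or post-randomization baseline radiological progression assessments": censored, end date is the date of randomization.
- **Death row**, "Death during the study (no 2 consecutive missing radiological assessments*) or before first radiological PD assessment": not censored, end date is the date of death.

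The footnote to the table reads: "Two consecutive missing radiological assessments are defined as the time interval between two consecutive radiological assessments is more than 28 weeks". The table gives no rule for a subject who meets more than one row.

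The corresponding row for SSE-FS, in Table 9-1 of Section 9.1.1, reads "No post-randomization SSE assessment and no death". Table 9-2 likewise limits its no-assessment row to subjects who have not died. Table 9-5 in Section 9.1.4, for time to radiological progression, opens with a row almost the same as row 1 of Table 9-7: "No randomization baseline or post-randomization baseline radiological assessment".

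**The concern.** A subject who dies before any post-baseline scan has no post-randomization radiological assessment, so row 1 applies. The same subject has died before a first radiological PD assessment, so the death row applies too. One row gives a censored time of one day and the other gives an event. The SAP leaves the choice to whoever programs the endpoint.

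If row 1 is used, the earliest deaths leave an endpoint that is meant to count them, and that censoring is informative. The trial is open-label and Section 4.4 allows interim results to be disclosed to the sponsor, so the choice should be fixed in the text and not left until data are in view.

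**Working it through.** There is no stated figure to reproduce. The check is to apply each rule to the same subject.

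**Subject 1: baseline scan done, death on day 40, no post-baseline scan**

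| Rule | Applies? | Result |
|---|---|---|
| Definition, Section 6.2.2.1 | Yes: death without prior progression | Event at death |
| Table 9-7, row 1 | Yes: no post-randomization assessment | Censored; end date − randomization date + 1 = 1 day |
| Table 9-7, death row | Yes: death before a first PD assessment | Event at death |
| Table 9-7, missed assessments (more than 28 weeks) | No: day 40 is under 6 weeks | Does not decide between the two rows |

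The death row's reference to a first PD assessment is loose. Whether it means before any assessment or before any assessment showing PD, it covers this subject.

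**Subject 2: no baseline scan, later death.** Row 1 censors this subject at randomization whenever the death occurs. The definition makes the death an event.

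**Comparison with the other tables.** In Table 9-5 a row of this kind is coherent, because death is not an event for time to progression. In Tables 9-1 and 9-2 death is an event, and the no-assessment row excludes subjects who died. In Table 9-7 death is an event, but that exclusion is absent.

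**Which comparison is affected.** Section 4.5.1 limits Comparison 2 to subjects with at least six injections. At one injection every 4 weeks, the sixth falls 5 × 4 = 20 weeks after the first. A death before a scan near Week 8 is therefore impossible in that set. What remains there is a subject with no baseline scan, or with no post-baseline scan despite six injections.

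**Size, as an illustration only.** The SAP gives no death rate. It does give planning medians for SSE-FS, and every death by a given date is also an SSE-FS failure by that date. The SSE-FS failures therefore set a ceiling on deaths under the planning model. Assumptions: constant hazards as in Sections 3.4 and 4.7.1, and a first scan at Week 8. Section 6.2.3.1.1 gives that timepoint for quantitative bone scans only, while the Table 9-7 footnote cites a 12-week tumor-assessment frequency.

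- t = 56 / 30.4375 = 1.84 months; share failing = 1 − exp(−ln 2 × t / median).
- Arms A and C, median 9 months: 13.2%, and 240 × 0.132 = 31.7 subjects.
- Arm B, median 13.5 months: 9.0%, and 120 × 0.090 = 10.8 subjects.
- Total: 42.5 of 360 with an SSE or death by Week 8.

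The share of these who die by Week 8 is not given. At assumed shares of 10%, 25% and 50%, about 4, 11 and 21 deaths would be events or non-events depending on the row applied.

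**The case against.** The strongest reply is that the SAP already shows its intention. The definition counts death from any cause, and the death row names the disputed case. A programmer who lets the specific row prevail over the general one reaches a single answer, an event at death. Letting row 1 prevail would leave the death row's second clause with little to do. As a statement of the likely intention this stands. It does not remove the defect, because row 1 as written still applies to these subjects and no precedence is stated.

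A reader might infer that row 1 must win because of the footnote to Tables 9-1 and 9-2: "The earliest end date in the table is used in calculating the SSE-FS". The documents do not support that. The footnote mark is attached only to the uncensored rows of the SSE-FS tables, it concerns SSE-FS alone, and Table 9-7 does not carry it.

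It is also fair to say that these deaths stay visible elsewhere. OS counts them. SSE-FS also counts a death before Week 8 that has no earlier SSE, because fewer than 13 weeks have passed since randomization. That limits the consequence for the trial as a whole, but it does not repair rPFS.

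**Conclusion.** The contradiction is real. Table 9-7 gives two results for a subject who dies without a post-baseline scan, or without a baseline scan, and row 1 conflicts with the SAP's own definition of rPFS. This follows from the text and needs no assumption about mortality. It touches one tested secondary endpoint and leaves the co-primary SSE-FS unaffected. Deaths before the first scan matter for Comparison 1; the exposure in Comparison 2 is limited to the residual cases described above.

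The number of subjects cannot be derived from the SAP. The range of about 4 to 21 of 360 rests on the planning hazards, a Week 8 first scan and assumed death shares.

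A reader might also infer that the plan flatters the high-dose arm. Nothing in the document says where early deaths will fall. If row 1 were applied, it would favour whichever arm has more of them; without an imbalance the main loss is of events. Nor does the plan prescribe that early deaths be dropped: it leaves the matter undecided.

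**What to change.** Limit row 1 of Table 9-7 to subjects who have no randomization baseline or no post-randomization radiological assessment and who have not died, using the same no-death condition as Table 9-1. State in the table that a death without a post-baseline scan is an event on the date of death.

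Then settle one further point. The 28-week interval in Table 9-7 runs between two radiological assessments, so it does not say how to treat a late death in a subject never scanned after randomization. If the missed-assessment rule is meant to cover such subjects, say that the interval is counted from the randomization date when there is no post-randomization scan. Footnote # of Table 9-1 already does this for SSE-FS. In Table 9-7 it would be a new rule and should be written as one.

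The cost is a phrase in one row, one sentence and, if wanted, one footnote. No new data are needed.
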